To further define the impact of NP in the peripartum period, we propose the following objectives:

- I. Characterize the course and pharmacological management of neuropathic pain in pregnancy and the postpartum period. We will define descriptive statistics of the use of analgesic medications in pregnancy and the postpartum period for the treatment of neuropathic pain.
- II. Compare obstetrical and neonatal outcomes of pregnant women with chronic neuropathic pain, non-neuropathic chronic pain, and pregnant women without chronic pain.
- III. Determine the acceptability and tolerability of rTMS for the treatment of neuropathic pain in pregnancy, and describe the impact of rTMS on neuropathic pain in pregnancy.

Subject Selection

Subjects will be enrolled through the Women's Mental Health Program (WMHP) at the University of Arkansas for Medical Sciences (UAMS) at the following clinical spaces: Psychiatric Research Institute (PRI); UAMS Women's Clinic (UWC); the Psychiatric Research Institute (PRI) inpatient units (PRI floors 5&6); and the UAMS Obstetrics & Gynecology units (UAMS floors 5,6, and 7A).

Protocol Title: Neuropathic Pain in Pregnancy
Institution: University of Arkansas for Medical Sciences (UAMS)
IRB Number: 204737
Sponsor: UAMS
PI: [name]

Study visits can occur at all of the above locations. For those subjects in part B, study visits will occur in a designated room designed for rTMS in the PRI. We aim to actively recruit and enroll 60 pregnant women and up to 70 infants (to allow for multiple gestation pregnancies) for Part A of this study and enroll 10 pregnant women and up to 15 infants (to allow from multiple gestation pregnancies) (from Part A) for Part B.

Compensation: Mothers participating in the study will receive a \$10 in cash for each visit. All participants will be given a token or voucher to pay for parking at each outpatient study visit when applicable.

Inclusion of Women, Minorities and Children

Women and adolescents between 18-45 years of age are eligible for participation in the current study. Every effort will be made to recruit a diverse population of women along racial and ethnic categories residing in underserved areas.

Eligibility Criteria

All women will provide consent and HIPAA authorization prior to enrollment in the study.

Part A:

Maternal Inclusion Criteria

- Age 18-45 years old,
- Ability to give informed consent,
- Viable pregnancy, and
- Enrollment prior to or equal to 24 weeks gestation

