Subjects will be identified by clinical staff based on current pregnancy status to identify potential subjects for the study. Once referred, initial screening by research personnel will include reviewing inclusion and exclusion criteria (as described in Eligibility Criteria) discussing the study, obtaining informed consent, completing the TASS questionnaire and initiating enrollment. These assessments and health related information will be collected on a paper form. All personnel will be qualified to administer all questionnaires.

Access to Medical Records: As a part of the informed consent for this protocol, individuals will allow the investigative team access to medical records. Any information acquired from medical records will be de-identified (no PHI, only subject ID code) and stored with the de-identified records obtained for this study.

The medical record will be utilized to gather obstetrical information regarding gestation and delivery of the infant, which may include but not limited to infant weight, height, APGAR scores, gender, head circumference, method of delivery and maternal or infant complications. Collection of health information will occur shortly following delivery of infant. Infants will only be assessed via medical records. There will be no direct assessment of infants within the scope of this study.

Questionnaires and Surveys for Parts A and B:

- Pain Interference Scale-Short Form 4a (Part A): This 4-item self-report scale measures the consequences of pain on relevant aspects of the subject's life. It includes impairment in the subject's social, cognitive, emotional, physical, and recreational activities. It also incorporates items about sleep and enjoyment of life. The short form is not disease specific and assesses pain interference over the past 7 days.
- Pain Behavior Scale-Short Form 7a (Part A): This 7-item, self-report scale measures behaviors that typically indicate to others that an individual is experiencing pain. These measures include observations (sighing, crying), behaviors (resting, guarding, facial expressions, asking for help), and verbal reports of pain. The short form is not disease specific and assesses pain interference over the past 7 days.

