All data will be kept either in locked file cabinets or password-protected computers accessible to only investigators or designated study staff. Trained study staff will enter data and original source documents will be stored in locked file cabinets in offices with limited access. A database will also be created to input subject information and only designated study staff will have access. Periodic reviews will occur to ensure that data is accurately entered and if needed, corrections can be made. The database will generate queries to account for missing information. Every subject enrolled in this study will be given a unique ID number that will be used for tracking purposes. The key linking the unique study ID number to identifiable information will also be stored in the password-protected computers accessible to only investigators or designated study staff. Each subject's name, SSN, birth date, address, phone number, and email address will be obtained for purposes of payment and follow-up. We will ask for each subject's drug use history, medical history, and current drug use.

Part A:

Descriptive statistics will be calculated for all measures obtained.

For the first hypothesis, primary outcome measures include VAS and pain assessments. Secondary outcome measures include BDI, PGIC, and CGI-I. For each outcome measure, scatter plots will be constructed for visual inspection across time by group. As outcome measures will be obtained at multiple time points, mixed models will be used to account for the correlations among the measurements within the subjects.

Table 3 provides a list of specific outcome data of interest for the second hypothesis. The occurrence of obstetrical outcomes will be compared between the three groups. If measures are normally distributed, we will use ANOVA to test the differences among the three groups. Otherwise, we will use a non-parametric method, such as Kruskal Wallis test, to test the difference among the groups.

Protocol Title: Neuropathic Pain in Pregnancy
Institution: University of Arkansas for Medical Sciences (UAMS)
IRB Number: 204737
Sponsor: UAMS
PI: [name]

Table 3: Specific Outcome Data

Obstetrical Records	Neonatal Records

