
• Preterm labor• Preterm birth• Premature rupture of membranes• Mode of delivery	
• 1 minute and 5 minute APGAR Scores• Length of Hospitalization• Neonatal Intensive Care Unit Admission• Neonatal Abstinence Syndrome• Birth weight and length• Gender

Part B (rTMS):

We will determine the acceptability of rTMS as a treatment option by determining the percentage of subjects who accept the treatment when offered. Tolerability will be determined by the reporting of adverse events. The primary outcome measure is VAS. Secondary outcome measures include BDI, PGIC, and CGI-I. For each outcome measure, scatter plots will be constructed for visual inspection across treatment. Using previous studies of rTMS for the treatment of neuropathic pain, we will determine an effect size and complete a power analysis. This information will help guide future studies of the effectiveness of rTMS in the treatment of neuropathic pain in pregnancy.

Neonatal outcomes will be analyzed between the following groups: 1. Subjects participating in rTMS (Part B); 2. Subjects with neuropathic pain who participated in Part A but did not participate in Part B; 3. Subjects with chronic non-neuropathic pain who participated in Part A; and 4. Subjects without chronic pain who participated in Part A. Specific endpoints of interest include neonatal intensive care unit admission, length of hospitalization, birth weight and length, and 1-min and 5-min APGAR scores. The occurrence of obstetrical outcomes will be compared between the groups. If measures are normally distributed, we will use ANOVA to test the differences among the three groups. Otherwise, we will use a non-parametric method, such as Kruskal Wallis test, to test the difference among the groups.

Neonatal outcomes will be scrutinized after each delivery and neonatal period. The investigator team will convene and review all neonatal outcomes to determine if any complication occurred that could be attributed to the study, participation in the study, and/or treatment received. If any complication is identified (i.e. preterm delivery with all subjects who participated in rTMS), we will cease all current and potential study procedures related to part B of the study.

All statistical analysis will be completed using SAS 9.4. Significance will be set at $p<0.05$.

Data Safety and Monitoring Plan

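### Infant outcomes are to be compared between groups with no stated unit of analysis, although multiple births are allowed; delivery levels and the Part B group count also need settling

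*Protocol*

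**What the plan says.** Subject Selection in the protocol sets the numbers: "We aim to actively recruit and enroll 60 pregnant women and up to 70 infants (to allow for multiple gestation pregnancies) for Part A". The same sentence gives 10 women and up to 15 infants for Part B.

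For the second hypothesis (Table 3), Statistical Methods and Data Management gives one rule in two branches, which the SAP repeats. The first branch is "If measures are normally distributed, we will use ANOVA to test the differences among the three groups". The fallback, for any measure that fails this condition, is "Otherwise, we will use a non-parametric method, such as Kruskal Wallis test, to test the difference among the groups". No unit of analysis is given for infant outcomes. The only correlation the section deals with is that of repeated pain and mood measures in one woman, where "mixed models will be used to account for the correlations among the measurements within the subjects".

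Table 3 lists "Mode of delivery" without levels. Access to Medical Records adds only "method of delivery and maternal or infant complications".

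For Part B, neonatal outcomes are compared across a numbered list that begins "1. Subjects participating in rTMS (Part B); 2. Subjects with neuropathic pain who participated in Part A but did not participate in Part B" and ends "4. Subjects without chronic pain who participated in Part A". That makes four groups. The test sentence that follows, in both documents, still refers to three. No particular contrast is named.

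Investigational Plan, Part A, obtains delivery and neonatal records only for women who delivered at UAMS.

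**The concern.** ANOVA and Kruskal-Wallis both treat every observation as independent. Siblings from one pregnancy are not: they share a mother, a gestational age and usually a discharge plan. Multiples also differ as a class from singletons in birth weight, length of stay and admission to intensive care. An infant-level analysis therefore goes wrong in two ways. It counts correlated infants as separate evidence, and it lets the share of multiples in a group pass for an effect of that group.

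These comparisons serve Objective II and supply the planned neonatal comparison for rTMS. In a group of 10 mothers, one or two multiple pregnancies are enough to matter. The plan also sets a 0.05 significance level, so the p-values will be read as such.

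**Working it through.** The documents give no SD, sibling correlation, event rate, group size or expected number of multiples, so there is no plan figure to reproduce. From the documents: 60 women and at most 70 infants; 10 women and at most 15 infants. Assumed: birth-weight SD 500 g, sibling correlation (ICC) ρ 0.4-0.6, all multiples twins, groups of 20/20/20 or 10/10/20/20 mothers, records on every mother.

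**Step 1, loss of information.** With W women, of whom P have twins, the variance of an infant-level mean is multiplied by D = [(W − P) + 2P(1 + ρ)] / (W + P).
- Two pairs among 60: D = (58 + 5.6)/62 = 1.03 at ρ = 0.4, and (58 + 6.4)/62 = 1.04 at ρ = 0.6.
- Ten pairs among 60 (the ceiling): D = (50 + 28)/70 = 1.11 and (50 + 32)/70 = 1.17.
- Five pairs among the 10 rTMS women (the ceiling): D = (5 + 14)/15 = 1.27 and (5 + 16)/15 = 1.40. Fifteen infants then carry the information of 15/1.27 = 11.8 and 15/1.40 = 10.7.

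**Step 2, approximate type I error.** For three groups the 5% critical value of chi-square on 2 df is 5.99, and the inflated error is about exp(−5.99/(2D)). This gives 5.4-5.6% for two pairs and 6.8-7.8% for ten.

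**Step 3, simulation of infant-level ANOVA on birth weight** (20,000 runs per cell, twin pairs placed at random, both group layouts):

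| Twin pairs | No twin deficit | Assumed 800 g deficit |
|---|---|---|
| 2 | 5.3-5.7% | 7.2-7.6% |
| 5 | 5.6-6.7% | 8.6-10.1% |
| 10 | 7.0-8.2% | 10.8-12.6% |

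The mother's mean with a singleton/multiple term holds 4.5-5.3% throughout. Shorter repeat runs agreed to within about one percentage point.

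**Step 4, shift in a group difference.** One twin pair among 10 rTMS mothers makes 11 infants, two of them twins. With no multiples in the comparator, an 800 g deficit moves the infant-level difference by 800 × 2/11 = 145 g. Averaging by mother alone still leaves 800 × 1/10 = 80 g, which is why the multiple term is needed.

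**Step 5, intensive care admission.** Assume 10% risk for singletons, 50% for each twin and latent sibling correlation 0.6. The chance that at least one twin is admitted is 1 − [1/4 + arcsin(0.6)/(2π)] = 0.648. One pair among 10 rTMS mothers and none among 10 comparators moves the crude risk difference by (0.648 − 0.10)/10 = 0.055; five pairs move it by 0.27. So the estimate must be stratified, as well as the test.

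**Step 6, mode of delivery.** Take an invented table of 60 women with three levels: 10/1/9, 14/5/1 and 12/4/4. Kruskal-Wallis gives p = 0.15, 0.86 or 0.009, depending only on how the levels are numbered. Pearson chi-square, which ignores order, is 10.27 on 4 df, p = 0.036. Collapsed to two levels, numbering no longer matters, but p is 0.44, 0.22 or 0.011 according to which level is set apart.

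**The case against.** The best reply on siblings is that 70 and 15 are upper limits. Few multiples, or none, may enrol, and with two pairs and no deficit the inflation is under one percentage point. That stands, and the larger figures are ceiling cases. It does not supply a unit of analysis, and one pair in the rTMS group already shifts the contrast.

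A reader might infer that the plan prescribes Kruskal-Wallis for every categorical outcome. It does not: the test is given as an example, and no categorical test is excluded. For yes/no outcomes the choice hardly matters, because the Kruskal-Wallis statistic is (N − 1)/N times Pearson chi-square. For delivery with three or more unordered levels, a coding fixed in advance keeps the test's size (5.1-5.2% in null runs). What remains open is what the result means and who chooses the coding. The spread in step 6 comes from one invented table and is not an expected effect.

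A reader might also infer that the plan acknowledges confounders and then ignores them. The text is narrower. Under Illicit Drugs, the remark about confounding attaches to prescription and non-prescription medications. The tobacco remark explains why women receive cessation information. A substance use disorder within the past year is an exclusion. The documents do not support a charge of neglected covariates, and none is made here.

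Finally, the mismatch in group count looks like text carried over from Part A; the numbered list makes the intention clear. It does not show that a group will be dropped.

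**Conclusion.** The gap is real and should be fixed: infant outcomes have no unit of analysis, and neither siblings nor multiple birth is allowed for. If infants are the unit, birth-weight type I error is roughly 5-6% with two twin pairs and 7-9% with ten, or about 7-8% and 10-13% with an 800 g twin deficit. All of this rests on an assumed SD, correlation, deficit and group sizes, and on records for all 60 mothers. Since records are limited to UAMS deliveries, the analysed number will probably be smaller and is unknown. The figures illustrate the mechanism and do not forecast this study's error rate. Confidence is high that the omission exists and low about its eventual size. The undefined delivery levels and the four-versus-three wording are minor.

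**What to change.** Amend the SAP, and the matching protocol text, as follows.

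1. Make the mother the unit for infant outcomes.
   - Continuous outcomes: the mother's mean with a singleton/multiple term, on ranks if clearly non-normal.
   - Intensive care admission and neonatal abstinence syndrome: whether any infant was affected, by a Cochran-Mantel-Haenszel test stratified by singleton/multiple. Report a risk difference stratified the same way, or for singletons if all multiples fall in one group.
   - State that multiples confined to one group add nothing to that contrast.
   - Report singletons only as a sensitivity analysis.
2. Define the delivery categories before data are seen and analyse them by Pearson chi-square with an exact or Monte Carlo p-value.
3. Write four groups in the Part B test sentence in both documents. Report rTMS versus neuropathic pain without rTMS as a descriptive, non-randomised estimate with a 95% CI.
4. State the number of deliveries with records as the denominator.

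The cost is wording and a few lines of SAS, with no new data. The downside is that an outcome of any infant affected is a risk per mother, not per infant. Intervals also stay wide. With 10 versus 10 mothers and no multiples, the birth-weight half-width is 2.101 × 500 × √0.2 = 470 g. Admissions in 2/10 versus 1/10 give a difference of 0.10 (−0.24 to 0.42, Newcombe score interval).

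### Table 3 records length of gestation only as preterm events and compares birth size without gestational age, so the plan has no continuous gestation outcome and no analysis that separates small from early infants

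*Protocol*

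**What the plan says.** Objective II compares obstetrical and neonatal outcomes between women with neuropathic pain, non-neuropathic pain and no pain. Table 3, identical in the protocol and the SAP, gives the outcomes. The obstetrical column reads "Preterm labor• Preterm birth• Premature rupture of membranes• Mode of delivery"; the neonatal column includes "Birth weight and length• Gender". Gestational age at delivery is in neither column.

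On analysis, the Part A text in Statistical Methods says "The occurrence of obstetrical outcomes will be compared between the three groups", and then "If measures are normally distributed, we will use ANOVA to test the differences among the three groups", with Kruskal-Wallis as the alternative. No covariate is named.

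For the four-group comparison in Part B, the text says "Specific endpoints of interest include neonatal intensive care unit admission, length of hospitalization, birth weight and length", followed by the two Apgar scores. That sentence contains neither preterm birth nor gestational age. Obstetrical outcomes return only in a general sentence, and preterm delivery appears as the example of a complication that would stop Part B.

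Two other places bear on whether the data exist. The eligibility criteria require "Enrollment prior to or equal to 24 weeks gestation", so every pregnancy is dated. Access to Medical Records says "The medical record will be utilized to gather obstetrical information regarding gestation and delivery of the infant", with a list of items that is explicitly open.

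**The concern.** Delivery at 36 weeks and 6 days and delivery at 28 weeks count the same on a preterm yes/no outcome, and 37 weeks counts the same as 41. With 60 women in three groups, few preterm births are likely, so most of what the women could show about gestation lies in the weeks, which the plan does not list.

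Birth weight and length depend strongly on when the infant is born. If mean weight is lower in one group, the planned unadjusted test cannot say whether its infants were born earlier or grew less. In Part B this matters more: admission to intensive care, length of stay, weight, length and Apgar scores all depend on gestation, yet no gestation measure stands beside them. If gestational age is brought in only after the results are seen, the analysis is post hoc.

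**Working it through.** **Inputs from the documents.** 60 women and up to 70 infants in Part A, 10 women in Part B (protocol, Subject Selection); three groups; ANOVA or Kruskal-Wallis; significance at 0.05 (taken as two-sided).

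**Not in the documents, so assumed.** Preterm proportion p, 5% to 20%; equal groups of 60/3 = 20 (real sizes will follow painDETECT scores); gestation with mean 39 and SD 1.8 weeks; preterm cut at 37 weeks. The plan gives no power figure for Objective II, so there is none to reproduce.

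**Step 1: information kept by the yes/no split.** For a normal variable that shifts between groups, the efficiency of the split relative to the full scale is φ(z_p)² / [p(1 − p)], where z_p is the normal quantile at p and φ the normal density.

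| p | φ(z_p)² | p(1 − p) | kept | lost |
|---|---|---|---|---|
| 5% | 0.0106 | 0.0475 | 22% | 78% |
| 10% | 0.0308 | 0.0900 | 34% | 66% |
| 15% | 0.0544 | 0.1275 | 43% | 57% |
| 20% | 0.0784 | 0.1600 | 49% | 51% |

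At 10%, 60 women carry about 60 × 0.342 = 20.5 women's worth of information on gestation. The loss applies to this outcome alone; birth weight, length and Apgar scores keep their full scale.

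**Step 2: power with the plan's own three-group tests.** Preterm proportion in the unshifted groups: Φ((37 − 39)/1.8) = Φ(−1.11) = 13%. In the shifted group: Φ((37 − 37.5)/1.8) = Φ(−0.28) = 39% for 1.5 weeks, and Φ((37 − 38)/1.8) = Φ(−0.56) = 29% for 1 week. Simulated power, 20 per group, one group shifted:

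| Shift | ANOVA on weeks | Kruskal-Wallis on preterm yes/no |
|---|---|---|
| 1.5 weeks | about 77% | about 50% |
| 1 week | about 40% | about 22% |

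**Step 3: does it depend on normality?** With a left-skewed gestation distribution (about 12% preterm, two groups of 20, 1.5-week shift), power was 84% with a rank test on weeks, 67% with a t-test on weeks, and 41% with a chi-square test on preterm yes/no. The direction holds, and ranks do better than means when there is a tail of early births.

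**Step 4: Part B.** For 10 against 10, even weeks give only about 22% power for a 1-week shift and 42% for 1.5 weeks.

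**Step 5: birth size.** Set side by side, Table 3 asks for raw weight and length, the test has no covariates, and no standardised or small-for-gestational-age measure is listed. No planned analysis combines size with gestation. Infant sex, needed to standardise size, is listed among the outcome data although maternal pain or rTMS during pregnancy cannot change it.

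**The case against.** The best reply is that gestation is not lost. The medical-records section gathers "obstetrical information regarding gestation and delivery of the infant" in an open list, and the plan promises descriptive statistics for all measures obtained. Preterm status and birth weight are both listed, so weight among term infants gives a crude separation of small from early. This stands as far as it goes: a reader might infer that the study throws gestational age away or cannot distinguish small from early infants, and the documents do not support that. They show that the data can probably be recovered but have no place in the analysis, and the term-only comparison is not planned.

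A reader might also state one fixed loss, such as two thirds. That follows only from a 10% preterm rate, which the documents do not give; the range above is the honest statement.

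A pairwise comparison with Fisher's exact test shows a wider gap: 72% against 35% for 1.5 weeks, and 40% against 14% for 1 week. The plan does not name that test, and it is conservative at 20 per group, so those figures overstate the gain.

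Finally, the study is small and its purpose largely descriptive. That also stands: 40% power for a 1-week shift, and the Part B figures, show that analysing weeks does not make these comparisons reliable. It does not justify choosing the weaker scale when the better one costs almost nothing. On infant sex, Table 3 can be read as a list of record items, so that point is minor.

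**Conclusion.** The concern holds in this form: the plan specifies no continuous gestation outcome, no gestation measure among the Part B specific endpoints, and no analysis that separates small from early infants, although gestational age is needed to call a birth preterm and information on gestation is gathered. The cost to the gestation comparison is roughly half to three quarters of its information if 5% to 20% of births are preterm, or some 18 to 27 percentage points of power in the three-group example. These sizes rest on an assumed preterm rate, mean and SD, equal groups and a simple shift; the direction also held in the skewed case. It is a worthwhile correction to the outcome list and does not by itself invalidate Objective II, which remains largely exploratory.

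**What to change.** - Add gestational age at delivery, in weeks and days, to Table 3 in both documents and to the Part B list of specific endpoints. Analyse it as continuous or by ranks, and keep preterm birth as a descriptive category.
- Report birth weight and length also as scores standardised for gestational age and sex, naming the reference standard in advance. Keep the raw values beside them: gestation may lie on the path from pain or its treatment to birth size, so the standardised result alone could hide a real effect.
- Flag multiple births or analyse them separately. The plan allows up to 70 infants from 60 women, and twins affect both gestation and size.
- Use infant sex for standardising and do not test it as an outcome (minor).

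The cost is a small amendment to protocol and SAP, which the protocol's monitoring section requires to go to the IRB, the choice of a reference standard, and one abstraction field that classifying preterm birth already needs. No extra women or visits are required.
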